8.6 Warnings and precautions

No evidence available at the time of the approval of this study protocol indicated that special warnings or precautions were appropriate, other than those noted in the provided [Investigator's Brochure]. Additional safety information collected between IB updates will be communicated in the form of Investigator Notifications. This information will be included in the patient informed consent and should be discussed with the patient during the study as needed.

8.7 Data Monitoring Committee

Not applicable.

8.8 Steering Committee

Not applicable.

9 Data collection and management

9.1 Data confidentiality

Information about study subjects will be kept confidential and managed under the applicable laws and regulations. Those regulations require a signed subject authorization informing the subject of the following:

- What protected health information (PHI) will be collected from subjects in this study
- Who will have access to that information and why
- Who will use or disclose that information
- The rights of a research subject to revoke their authorization for use of their PHI.

In the event that a subject revokes authorization to collect or use PHI, the investigator, by regulation, retains the ability to use all information collected prior to the revocation of subject authorization. For subjects that have revoked authorization to collect or use PHI, attempts should be made to obtain permission to collect at least vital status (i.e. that the subject is alive) at the end of their scheduled study period.

The data collection system for this study uses built-in security features to encrypt all data for transmission in both directions, preventing unauthorized access to confidential participant information. Access to the system will be controlled by a sequence of individually assigned user identification codes and passwords, made available only to authorized personnel who have completed prerequisite training.

9.2 Site monitoring

Before study initiation, Novartis personnel (or designated CRO) will review the protocol and eCRFs with the investigators and their staff. During the study, the Investigator or designee will enter all required patient data into the eCRF within 72 hours (3 days) of the patient visit. The field monitor will visit the site regularly to check the completeness of patient records, the accuracy of entries on the eCRFs, the adherence to the protocol to Good Clinical Practice, the progress of enrollment, and to ensure that study treatment is being stored, dispensed, and accounted for according to specifications. Key study personnel must be available to assist the field monitor during these visits.

The investigator must maintain source documents for each patient in the study, consisting of case and visit notes (hospital or clinic medical records) containing demographic and medical information, laboratory data, electrocardiograms, and the results of any other tests or assessments. All information recorded on eCRFs must be traceable to source documents in the patient's file. The investigator must also keep the original signed informed consent form (a signed copy is given to the patient).

The investigator must give the monitor access to all relevant source documents to confirm their consistency with the eCRF entries. Novartis monitoring standards require full verification for the presence of informed consent, adherence to the inclusion/exclusion criteria and documentation of SAEs. Additional checks of the consistency of the source data with the eCRFs are performed according to the study-specific monitoring plan.

9.3 Data collection

This study will use Electronic Data Capture (EDC) and the designated investigator staff will enter the data required by the protocol into the eCRF. The eCRFs have been built using fully validated secure web-enabled software that conforms to 21 CFR Part 11 requirements. Investigator site staff will not be given access to the EDC system until they have been trained. Automatic validation programs check for data discrepancies in the eCRFs and, allow modification or verification of the entered data by the investigator staff.

The Principal Investigator is responsible for assuring that the data entered into eCRF is complete, accurate, and that entry and updates are performed in a timely manner.

Mutational analysis data will be generated by CLIA certified local labs. We anticipate that the data available in the report will vary from lab to lab. [REDACTED]

If a tumor sample is obtained at the time of disease progression (optional), data about the sample will be collected in the eCRF.

Laboratory assessments for hematology, biochemistry, coagulation, urinalysis, MUGA and ECGs will be collected locally and entered directly onto the eCRFs.

9.4 Database management and quality control

This study will be using eCRFs and the designated CRO will review the data entered by investigational staff for completeness and accuracy. Electronic data queries stating the nature of the problem and requesting clarification will be created for discrepancies and missing values and sent to the investigational site via the EDC system. Designated investigator site staff are required to respond promptly to queries and to make any necessary changes to the data.

Concomitant treatments and prior medications entered into the database will be coded using the WHO Drug Reference List, which employs the Anatomical Therapeutic Chemical classification system. Medical history/current medical conditions and adverse events will be coded using the Medical dictionary for regulatory activities (MedDRA current version) terminology.

Data from the screening molecular analysis will be collected locally and entered directly onto the eCRF. [REDACTED]

At the conclusion of the study, the occurrence of any protocol deviations will be determined. After this action has been completed and the data has been verified to be complete and accurate, the database will be declared locked and the data made available for data analysis. Authorization is required prior to making any database changes to locked data, by joint written agreement between the US Oncology Medical Affairs Franchise Head and the US Oncology Medical Affairs Franchise Vice President.

After database lock, the investigator will receive a CD-ROM or paper copies of the patient data for archiving at the investigational site.

10 Statistical methods and data analysis

All data except the primary efficacy variable clinical benefit rate will be analyzed by a designated CRO in collaboration with Novartis. Any data analysis carried out independently by the investigator should be submitted to Novartis before publication or presentation. The data from all centers that participate in this study will be combined in the final safety and efficacy analysis.

10.1 Analysis sets

10.1.1 Full Analysis Set

The Full Analysis Set (FAS) will include all patients who have received at least one dose of study drug.

FAS will be used for the analysis of efficacy endpoints.

10.1.2 Safety Set

The Safety Set will include all patients who received at least one dose of study treatment and had at least one post-baseline safety assessment.

Please note: the statement that a patient had no adverse event (on the Adverse Event eCRF) constitutes a safety assessment.

10.2 Patient demographics/other baseline characteristics

Demographic and other baseline data (including disease characteristics) will be listed and summarized by patients groups formed by the type of cancer at study entry using the FAS (See [Appendix Q](#) for predicted target cancer population). Additional groups may be added based on enrollment (See [Appendix Q](#)). Categorical data, such as gender, race, etc., will be presented by frequencies and percentages. Descriptive summary statistics (e.g., frequency, mean, median, range and standard deviation) will be used to present numeric data.

10.3 Treatments (study treatment, concomitant therapies, compliance)

10.3.1 Study medication

Duration of study treatment exposure, cumulative dose and dose intensity will be summarized by the patient groups as above using the Safety Set. The number of patients with dose changes/interruptions will be presented along with reasons for the dose change/interruption. The safety set will be used for the tables and listings.

10.3.2 Concomitant therapies

Concomitant medications and significant non-drug therapies taken concurrently with the study drugs will be listed and summarized for the FAS by Anatomical Therapeutic Chemical Classification System (ATC) term, preferred term and treatment arm by means of frequency counts and percentages. These summaries will include medications starting on or after the

start of study treatment (defined as cycle 1 day 1) or medications starting prior to the start of study treatment and continuing after the start of study treatment.

Any prior concomitant medications or significant non-drug therapies starting and ending prior to the start of study treatment will be listed. The safety set will be used for all above mentioned concomitant medication tables and listings.

10.4 Primary objective

The primary objective is to assess clinical benefit associated with ceritinib treatment based on local investigator assessment.

For patients with solid tumors the assessment criteria will be RECIST 1.1 and will include responses of CR or PR or SD \geq 16 weeks. For hematologic tumors other appropriate hematological response criteria will apply and are included in the appendices.

For solid tumors, an assessment of CR or PR using RECIST 1.1 must be confirmed at least 4 weeks after initial observation, If the two assessments differ, the best response will be determined by [Table 14-5](#) of Appendix A.

10.4.1 Variable

The primary efficacy variable is the clinical benefit rate (CBR) (e.g. defined as CR or PR or SD \geq 16 weeks for solid tumors).

10.4.2 Statistical hypothesis, model, and method of analysis

The study will enroll patients from at least 6 histologic groups. In addition, another group simply referred to as “Other” may be identified and enrolled throughout the study.

We let Y_i be the response indicator for the i^{th} subject, and let R_g be the assumed probability of response within a control population and $\pi_g = \Pr(Y_i = 1 | g_i = g)$ be the underlying probability of response for group g within the treatment group. We transform to the logit scale for modeling purposes. Let θ_g be the mean log odds treatment effect, i.e.:

$$\theta_g = \log\left(\frac{\pi_g}{1 - \pi_g}\right) - \log\left(\frac{R_g}{1 - R_g}\right).$$

Thus, θ_g is the group specific logistic regression coefficient for the treatment within group g . The primary analysis is a set of group specific tests that $\theta_g > 0$, meaning that the treatment is better than the assumed control rate within that group. Thus, we wish to test the set of hypotheses

$$H_0g : \theta_g \leq 0$$

$$H_1g : \theta_g > 0$$

We proceed in a Bayesian fashion, assigning a prior distribution (details in [Appendix Q](#)) and computing the posterior probability of H_1g within each group g . If, at the final analysis,

$$\Pr(\theta_g > 0 | \text{data}) > 0.90$$

Then group g will be declared a success (thus, the final analysis produces a separate decision for each group). The trial also allows for early stopping of groups, described below.

The statistical design borrows information across groups with a hierarchical model. The hierarchical model allows dynamic borrowing of information between groups such that more borrowing occurs when the groups are consistent and less borrowing occurs when the groups differ. In this way, the model is a compromise between the two alternate extremes of either a completely pooled analysis or a separate analysis in each group.

The purpose of such an analysis (discussed in more detail in the [Appendix Q](#)) is to produce higher power or lower type I error in situations where we see some commonality (identical effects are not required) among the groups. Details of the hierarchical model is provided in [Appendix Q](#).

10.4.3 Evaluation of trial success and futility

The clinical benefit rate will be evaluated for futility and early success by comparing posterior quantities for the rate to pre-specified early stopping criteria. The evaluations are planned to occur after the first 30 patients are dosed for at least 16 weeks or discontinued, then every 13 weeks thereafter until the enrollment closure of the study. An additional CBR evaluation will be performed after the database lock for the primary CSR.

Early Futility

If there is less than 10% probability that the response rate in a group exceeds the historical rate R_g , then the group will stop enrollment early for futility. Formally, enrollment will stop early for futility if:

$$\Pr(\pi_g > R_g) < 0.10.$$

A group is only eligible for early stopping once a minimum of 10 patients has been evaluated for response in that group.

Early Success

If there is at least 95% probability that the response rate in a group exceeds the historical rate, then the group will stop enrollment early for success. Formally, enrollment will stop early for success if:

$$\Pr(\pi_g > R_g) > 0.95.$$

A minimum of 15 subjects will need to be evaluated prior to declaring a group to be efficacious.

Final Analysis

The final analysis will occur when both accrual and follow-up are complete in all groups. If, at the completion of the trial, there is at least 90% probability that the response rate in a group exceeds the historical rate, then the group will be considered a success. Formally if:

$$\Pr(\pi_g > R_g) > 0.90.$$

In addition, a group will be considered as “promising” if:

$$0.80 < \text{Pr}(\pi_g > R_g) < 0.90.$$

10.4.4 Handling of missing values/censoring/discontinuations

A patient who has not progressed or died at the date of the analysis cut-off would have his/her PFS and OS censored at the time of the last adequate assessment before the cut-off date. Any disease assessment indicating response status other than “unknown” or “not done” is considered an adequate response assessment.

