10.5.2 Other secondary efficacy objectives

The secondary objectives of the study:

- To assess progression free survival (PFS) based on local investigator assessment per RECIST 1.1 or other appropriate hematological response criteria
- To assess overall survival
- To assess duration of response (DOR) based on local investigator assessment per RECIST 1.1 or other appropriate hematological response criteria
- To assess safety and tolerability

The secondary efficacy variable progression free survival (PFS) is defined as the time from the date of first dose to the date of first documented disease progression or relapse or death due to any cause.

PFS will be summarized and graphed using the Kaplan-Meier product-limit method for the entire study cohort. For cohorts with at least 10 subjects, separate PFS analyses will be conducted for each cohort. Patients who drop-out without progression will be censored at the time of last adequate assessment. The estimates of the 25th, median, 75th percentiles of the PFS and their 95% confidence intervals will be provided, if applicable.

Overall survival (OS) is defined as the time from the date of first dose to the date of death due to any cause. If a patient is not known to have died, survival time will be censored at the date of the last contact.

OS will be summarized and graphed using the product-limit method as above.

The duration of response applies only to patients whose best response was PR or CR. For patients with solid tumors the assessment criteria will be RECIST 1.1 and will include responses of CR and/or PR. For hematologic tumors other appropriate hematological response criteria will apply and are included in the appendices. The duration of response is defined as the time from the first documented response to the date first documented disease progression or relapse or death due to any cause. The duration of response will be summarized descriptively for the entire study cohort.

If the study primary efficacy endpoint is not met, Novartis may decide not to conduct some of the above secondary efficacy analyses but instead provide those endpoints in listings only.

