14.1.2.2.3 New lesions

The appearance of a new lesion is always associated with Progressive Disease (PD) and has to be recorded appropriately in the eCRF.

- If a new lesion is **equivocal**, for example because of its small size, continued therapy and follow-up evaluation will clarify if it represents truly new disease. If repeat scans confirm there is definitely a new lesion, then progression should be declared using the date of the first observation of the lesion.
- If new disease is observed in a region which **was not scanned at baseline** or where the particular baseline scan is not available for some reason, then this should be considered as

a PD. The one exception to this is when there are no baseline scans at all available for a patient in which case the response should be UNK, as for any of this patient's assessment.

- A **lymph node is considered as a “new lesion”** and, therefore, indicative of progressive disease if the short axis increases in size to ≥ 10 mm for the first time in the study plus 5 mm absolute increase.
 - a. Negative FDG-PET at baseline, with a positive¹ FDG-PET at follow-up is a sign of PD based on a new lesion.
 - b. No FDG-PET at baseline and a positive FDG-PET at follow-up: If the positive FDG-PET at follow-up corresponds to a new site of disease confirmed by CT, this is PD. If the positive FDG-PET at follow-up is not confirmed as a new site of disease on CT, additional follow-up CT scans are needed to determine if there is truly progression occurring at that site (if so, the date of PD will be the date of the initial abnormal FDG-PET scan). If the positive FDG-PET at follow-up corresponds to a pre-existing site of disease on CT that is not progressing on the basis of the anatomic images, this is not PD.

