14.2.4.1.3 Evaluation of response for all index lesions

The evaluation of response for all index lesions is based on the combination of the response for index nodal lesions (CR or non-CR), the response for index extranodal and the status based on the SPD calculated on all index lesions (nodal and extranodal), as described in [Table 14-9](#).

Table 14-9 Radiological response for index lesions

Response for index nodal lesions ¹	Response for index extranodal lesions ¹	Status based on SPD calculation for all index lesions	Response for index lesions
CR	CR	Not calculated	CR
CR	SD/ PR	Not calculated	PR
CR	PD	PD	PD
CR	PD	PR	PR
CR	PD	SD	SD
Non-CR	Not evaluated	PD	PD
Non-CR	Not evaluated	PR	PR
Non-CR	Not evaluated	SD	SD

¹ If no index nodal lesions are present at Screening, then index lesions response is equal to the index extranodal lesions response. A similar rule applied if no index extranodal lesions are present at Screening, then index lesions response is equal to the index nodal lesions response.

In case of missing measurements of any of the index lesions, the radiological response for index lesions at that assessment will be “Unknown (UNK)”, unless progression was seen.

All lesions must have been measured with the same method as the one used at Screening, otherwise the radiological response for index lesions at that assessment will be “Unknown (UNK)”.

14.2.4.1.4 Evaluation of non-index lesions (including nodal, splenic and/or hepatic nodules and other extranodal lesions)

At each reassessment, a non-index lesion (or a group of non-index lesions) will be given one of the following designations:

- Normalization (non-index nodal lesion has regressed to normal size; non-index extranodal lesion is no longer present). Normalization of non-index nodal lesions should be determined based on their size at Screening.
- Improved, stable or worsened, but without unequivocal evidence of disease progression (non-index lesion is present but there is not sufficient worsening to declare PD based on the existing non-index lesions).
- Unequivocal evidence of disease progression (worsening of existing non-index lesions is sufficient to declare PD).
- Not assessed.

Then, this status for each non-index lesion (or group of non-index lesions) will lead to a global response for non-index lesions ([Table 14-10](#)):

Table 14-10 Response criteria for non-index lesions (nodal, splenic and/or hepatic nodules and other extranodal lesions)

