The primary efficacy objectives of the study, clinical benefit (definition details see Section 6.1) associated with ceritinib treatment based on local investigator assessment, will be summarized. The clinical benefit rate will be analyzed using a Bayesian hierarchical model to evaluate trial success and futility, and the relationship between relevant pathway regulation and the response to treatment with ceritinib (if applicable). Analysis details are documented in Section 10.

Duration of response (DOR) based on local investigator assessment will be analyzed. In the event of a low response rate, DOR will be listed only without frequency summaries. Overall response (OR) will be summarized with the number and percentages of subjects for each response category (e.g., for solid tumor - CR, PR, SD, PD, Not evaluable). Progression-free survival (PFS) will be summarized using Kaplan-Meier (KM) methodology. Due to limited survival follow-up for the study, overall survival will only be descriptively summarized, ie, only the frequency of deaths will be provided.

Subject demographics, disease characteristics (including mutation analyses), ceritinib treatment, and safety variables will be summarized descriptively, by nominal visit (if applicable), and/or overall.

Data used for the analyses specified in this document will come from the Electronic Data Capture (EDC) system. In addition, the mutation data from the central laboratory will be collected in an Excel spreadsheet format and subsequently be uploaded to a secure FTP site by Novartis.

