6.3 Progression Free Survival (PFS)

PFS is defined as the time from the date of first dose of ceritinib to the date of the first documented disease progression/relapse or death due to any cause within 30 days of the last dose, and is calculated as $PFS = (\text{date of progression/relapse or death} - \text{date of first study treatment} + 1)$. Disease progression noted as the reason for discontinuation of treatment will be considered as a progression, thus will be considered as an event for PFS.

Subjects who discontinue or complete study treatment without disease progression will be censored at last adequate tumor assessment on or before the discontinuation/completion of the study. If there is no tumor assessment for the subject, the PFS will be censored at Day 1.

PFS will be summarized and graphed using the Kaplan-Meier product-limit method¹. The estimated median survival time, the corresponding 95% CIs², and 25th and 75th percentiles will be provided. In addition, survival rate estimates at 1, 2, 3, 4, 5, 6, and 12 months with 95% CIs will also be provided. For cohorts with at least 10 subjects, separate PFS analyses will be conducted for each cohort.

The above analyses will be performed for the FAS.

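### The definition of an adequate assessment leaves out NE, so an unevaluable last solid-tumor scan can set the PFS censoring date and move the PFS estimate upward (minor)

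*Protocol*

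**What the plan says.** **Definition.** Protocol 10.4.4 states: "Any disease assessment indicating response status other than “unknown” or “not done” is considered an adequate response assessment". It applies this to a patient without an event, who "would have his/her PFS and OS censored at the time of the last adequate assessment before the cut-off date".

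**Use.** Protocol 10.5.2 repeats the PFS rule: "Patients who drop-out without progression will be censored at the time of last adequate assessment". SAP 6.3 says that patients who stop or complete treatment without progression "will be censored at last adequate tumor assessment on or before the discontinuation/completion of the study", and puts the censoring date at Day 1 if the patient has no tumor assessment. SAP 2.1 has a matching sentence directly after its statement on duration of response (DOR). Neither SAP section defines 'adequate'.

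**Status labels, solid tumors.** Table 14-3 in Appendix A gives NE as the overall response when target lesions are not all evaluated, non-target lesions show no PD and there is no new lesion. Appendix A uses UNK for something else, namely "when there are no baseline scans at all available for a patient in which case the response should be UNK". SAP section 2 plans counts "for each response category (e.g., for solid tumor - CR, PR, SD, PD, Not evaluable"; its example list has no 'unknown' category.

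**Status labels, lymphoma.** Protocol 14.2.4.1.3 says: "In case of missing measurements of any of the index lesions, the radiological response for index lesions at that assessment will be “Unknown (UNK". The only exception there is a scan that shows progression. Protocol 14.2.4.2.1 carries that label through to the overall response.

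**The concern.** A scan with unevaluated target lesions has not excluded target-lesion progression. Censoring a patient at that scan keeps the patient in the risk set as progression-free for up to one more scan interval, while evaluable patients are recorded as progressing at the same visit. The denominator is larger than the evidence supports.

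The wording also treats like scans differently. An incomplete lymphoma scan without progression is UNK and cannot set the censoring date; an incomplete solid-tumor scan without progression is NE and can. Both kinds of patient enter the same whole-cohort Kaplan-Meier curve.

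At stake is the PFS estimate, overall and in any cohort of at least 10 patients, where one or two such patients could be visible. No success, futility or stopping decision uses PFS.

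**Working it through.** The documents state no figure that depends on this rule, so there is none to reproduce. The check has three parts.

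**1. Does an NE scan meet the definition?** The excluded statuses are 'unknown' and 'not done'. NE is a separate status in Appendix A, where UNK is assigned only when baseline scans are absent. Followed literally, NE is adequate, and no SAP text changes that.

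**2. Can later data correct the date?** Often, but not always.
- Efficacy follow-up is marked not applicable (Protocol 7.1.4.2). SAP 2.1 notes that post-treatment tumor assessments are not collected and that deaths more than 30 days after treatment are not PFS events.
- Table 7-1, footnote 3, requires an end-of-treatment scan when the previous scan showed no PD and was at least 8 weeks earlier (±4 days). A patient who stops for toxicity or withdrawal sooner than that after an NE scan need not have another.
- An evaluable scan afterwards, progression recorded as the reason for stopping (an event under SAP 6.3), or death within 30 days of the last dose removes the effect.

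The affected patients are therefore those with no PFS event whose last scan is NE.

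**3. Direction and size.** Each Kaplan-Meier factor is 1 − d/n. Moving a censoring time later leaves d unchanged and can only raise n, so the curve cannot fall. Example: 40 at risk at a scan visit, 16 events, and 4 of the 40 rated NE with no later data.
- NE counted as adequate: 1 − 16/40 = 0.600
- NE not counted: 1 − 16/(40 − 4) = 1 − 16/36 = 0.556

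This is the largest difference for those counts, because it assumes that the NE patients are at risk for every event at the visit.

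For an average size, cohorts were simulated with N = 80 (within the planned 70-90) and scans every 8 weeks (Protocol 4.1.1). Assumed, because the documents do not give them:
- exponential PFS with a median of 2, 4 or 8 months;
- a probability per scan of 2%, 5%, 10% or 20% that the scan is NE and the patient then leaves without an event, independently of progression;
- all scans on the scheduled day.

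There were 1,000 cohorts per setting. The true value is exp(−ln 2 × 16 / median in weeks), with median in weeks = months × 52/12. Cells show mean 16-week PFS with NE counted / not counted, and the difference taken before rounding.

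| Final NE per scan | Median 2 months (true 0.278) | Median 4 months (true 0.527) | Median 8 months (true 0.726) |
|---|---|---|---|
| 2% | 0.286 / 0.276 (0.010) | 0.534 / 0.526 (0.008) | 0.729 / 0.724 (0.005) |
| 5% | 0.301 / 0.276 (0.025) | 0.547 / 0.527 (0.021) | 0.739 / 0.727 (0.013) |
| 10% | 0.330 / 0.278 (0.052) | 0.570 / 0.529 (0.041) | 0.752 / 0.727 (0.025) |
| 20% | 0.386 / 0.278 (0.108) | 0.610 / 0.528 (0.082) | 0.779 / 0.728 (0.051) |

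The estimate with NE counted was never the lower one in any simulated cohort. In a further simulation with the ±4-day window, an assumed 12-week median and 10% final NE, 16-week PFS was 0.422 counted and 0.381 not counted, against a true value of about 0.39. With the window, excluding NE lands slightly low, but closer than counting it.

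**The case against.** **'Unknown' may have been meant to include NE.** Section 10.4.4 covers all tumor types, and the lymphoma, AML, ALL and CML appendices use Unknown for an incomplete or unreadable assessment. In the protocol's own summary of earlier solid-tumor data (Table 1-2), 35 of 246 patients fall under Unknown and there is no NE row. This reading is plausible. No passage states it, though, and Appendix A separates the two labels, so a programmer following the text would count NE. The ambiguity stands as a reason to fix the wording, not as proof of how the analysis will be run.

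**Inflation is not established.** A reader might infer that PFS is inflated. The documents support only that it can be. The effect needs event-free patients who end on an NE scan, and 8-weekly scanning, prompt assessment of suspected progression (Protocol 7.2.1), the end-of-treatment scan and the SAP 6.3 event rule all narrow that group. The higher assumed rates in the table have no basis in the documents.

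**An NE scan is not empty.** Under Table 14-3 it requires non-target disease without PD and no new lesion, so it is partial evidence against progression. That is correct, but Appendix B has similar partial evidence for lymphoma and still calls the scan UNK.

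**The Day 1 rule in SAP 6.3 is not breached.** It applies only when there is no tumor assessment. A patient whose sole post-baseline scan is NE has had one, so crediting about 8 weeks follows the text. Day 1 for that patient is a proposed extension.

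**DOR is hardly involved.** Section 10.4.4 does not name it. It is reached only through SAP 2.1, is summarized descriptively and is merely listed if responses are few. Neither document plans Kaplan-Meier or by-cohort DOR, so a claim that such curves are biased has no support.

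**Conclusion.** The gap is real and minor. As worded, a solid-tumor NE scan is adequate and can set the PFS censoring date, while the comparable lymphoma scan cannot, and the SAP does not close the gap. Any effect on the Kaplan-Meier PFS estimate is upward. On assumed rates it averages about 0.5 to 1 percentage point at week 16 with 2% final NE per scan, and about 5 to 11 points with 20%; it is zero if no censored patient ends on NE. These sizes rest on exponential PFS, NE independent of progression and no later data after the NE scan.

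The primary clinical benefit rate has its own handling in SAP 6.1 and is unaffected. PFS carries no hypothesis test, and DOR is touched only descriptively. Section 10.4.4 also applies its rule to OS, where 10.5.2 uses last contact; that is not pursued here because SAP 6.4 now reports only death counts.

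**What to change.** In Protocol 10.4.4, and by the same words in SAP 2.1 and 6.3, state that assessments rated NE, unknown (UNK) or not done are not adequate, so that censoring falls at the last assessment with CR, PR, SD, non-CR/non-PD or the disease-specific equivalent. Name PFS and DOR as the endpoints to which this applies.

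In SAP 6.3, extend Day 1 censoring from patients with no tumor assessment to patients with no adequate post-baseline tumor assessment.

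The cost is a sentence or two in each document and a small change to the censoring derivation. No new data are needed. Reported PFS may be slightly lower.
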